Quality of life will be measured on the World Health Organization Quality of Life (WHOQOL) – BREF and change in every day activities on the Alzheimers' Disease Cooperative Study MCI Activities of Daily Living Scale (ADCS-MCI-ADL)[Galasko *et al.* 1997].

4. Measure of brain activation /perfusion with near infrared spectroscopy heamoenephalography (NIRS-HEG)

We will collect brain activation data from all participants at the three time points during administration of the divided attention paradigm which runs for 5 minutes.

We will use a CE marked Oxymon Mk (Artinis, Netherlans) to measure changes in light attenuation at four discrete wavelengths (775,825,,850 and 905 nm) using four laser diodes as light sources and photon multiplier tube as detector. Sensors will be placed over the left prefrontal (F3), the superior parietal (P3) and the occipital cortex (O1) and the right frontal pole (Fp2), according to the international 10-10 system developed for EEG. This portable system does not involve any ionising radiation.

Treatment sessions

1. Physical exercise

Participants will be asked to complete 36 training sessions at a frequency of two to three per week. Half of all the groups (Feedback participants, **FP-group**) will be randomly allocated sound and vibration feedback to help them to stay in a predetermined training zone. Heart rate for the moderate training zone (less than 60% of VO2 max; 65-77% of maximum heart rate) will be determined for each participant from their predicted maximum heart rate (HR max = 220 – age). The other groups will not receive feedback but heart rate will still be measured (Monitoring participants, **MP-group**); this group will receive instruction on utilising subjective reports of effort to guide their optimal level of effort. Assignment to FP-group and MP-group will alternate so equal numbers are obtained for statistical comparison. In addition each participant will be issued

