with a large poster providing visual instructions of how to use the equipment and do a 10 minute warm-up routine (Appendix B). They will receive home visits and supervision at sessions 1, 3, 8, 14 and 20 (see Appendix C for a timelines). They will also receive regular weekly telephone contact to provide support and monitor progress. Heart rate monitors (Oregon Scientific SE102I) measure electrocardiographic signals via a chest strap. Heart rate zones are programmed into the monitors and auditory signals and vibration of the monitor attached to the arm provides feedback and alerts the patient when heart rate is outside the preset parameters. Heart rate monitors will be programmed by the research team. An electronic data logger (Oregon Scientific WM100) which collects continuous data from the chest strap will be activated during activity so that heart rate data during physical activity is captured for later analysis.

Patients taking beta blocker medication will exercise at a heart rate equivalent to a specific effort (14 on the Borg scale) as these medications lower heart rate and result in sub optimum training when training zones are calculated as described above [Tabet *et al.* 2008;Borg 1970]. The relevant rate will be determined during the initial supervised walking sessions.

2. Cognitive training

In addition to Physical exercise participants will be asked to complete 12 cognitive training sessions at a frequency of 1-2 per week. Training will take place on an individual and group basis, both supervised and unsupervised. The duration of training sessions will vary from 30 to 90 minutes depending on the type of training. A variety of training techniques will be employed with the aim to improve specific cognitive components such as attention, speed of processing, working memory, problem solving and reasoning. For training we will use the program developed by Lumosity (www.lumosity.com). Centre-group participants will have access to online resources either at training centres provided and staffed by the Adult Community Learning (ACL) Service in Essex, or at home. Online-group participants will be provided with access to computers and the internet for the duration of the study. These participants will not require any existing computing skills as all content will be accessed and supervised remotely by the researchers and ACL staff. Participation on the cognitive Lumosity program will be anonymised and data will be collected on the time and duration

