of activity as well as performance. The Lumosity program provides feedback on performance and participants can do additional activities if they choose.

3. Socialising

Socialising will take place in groups of 8 for the centre based participants. Participants will attend for 12 weeks, a 2.5 hour long session at facilities provided by ACL Essex. All sessions will broadly follow the same format.

0-15 Minutes: Greeting and light chair based balance and stretching activities. These activities will be lead by a video prompt (video: Active Health 50+ from *Age Concern*) and monitored by research staff.

15-45 Minutes: Reporting on and presentation of completed tasks from previous week and advice on practicalities of tasks.

45 - 60 Minutes: Break

60 to 120 Minutes: Group based creative or physical activity.

120 to 150 Minutes: Feedback and relaxation training (video guided relaxation)

The first two group sessions will be used to introduce participants to each other and familiarise them with computers and using a mouse to facilitate the cognitive training sessions. The sessions will be lead by trained tutors and detailed instructions on the scope and sequencing of activities will be provided in a training manual. Creative and physical activities included are designed to stimulate cognition and emphasis is placed on variety and multi-sensory stimulation. Home activities described in detail in Appendix D. Group based activities described in detail in Appendix E.

Motivating adherence.

Participants will be made aware that specific persuasion techniques will be implemented to improve their long term commitment to physical activity, cognitive stimulation and socialising. These will include the principals of reciprocity, authority, scarcity, liking and social proof.

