Feeling very hot and perspiring profusely

Dehydration

Getting lost

Confusion

Wandering

Lack of coordination

Increased recovery time

Cognitive activity related

Headache Fatigue Wrist pain/strain from using mouse

Eye strain

Social activity related

Feelings of frustration Social anxiety

Ethical approval

Ethical approval will be sought for the study from the local research ethics committee.

Statistical analysis

Subjects will serve as their own controls and data will be captured at baseline, following 12 weeks of DSD and at the end of phase two (study week 26). Continuous variables will be compared using paired t-tests and analyses of variance. All statistics will be analysed using SPSS / PC+ version 10.0 (Statistical Package for Social Sciences).

Sample Size.

The planned sample size (n=128) will enable us to detect a change of 0.25 standard deviations in the performance outcomes (details here) with 80% power at the 5% level of significance. The planned comparison between the community based /centre based groups (n=64) will enable us to detect a 0.5SD difference with 80% power at 5% significance. In this feasibility study, it is unlikely that this scale of change will be observed. More important will be our ability to estimate the potential size of the changes. In this case, with 128 subjects we can estimate the change to within +/- 17.5%SD (i.e. the width of the 95% CI will be 35%SD).

Analysis

The principle analysis will focus on the estimation of the change resulting from the intervention. This will be estimated by mean change and 95% CI. Supplementary analyses will employ Repeated Measures ANOVA to examine the changes from Baseline, start of therapy to the end of therapy. These analyses will be extended to assess the role of background covariates, such as age, sex health status etc. Abbott RD, White LR, Ross GW, Masaki KH, Curb JD, Petrovitch H. Walking and dementia in physically capable elderly men. JAMA 2004; 292: 1447-1453.

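### Heart-rate feedback is said to be both randomly allocated and alternated; alternation is predictable, so the subsidiary FP v MP comparison is open to selection bias

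*Protocol*

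**What the plan says.** The allocation is described in one paragraph of the protocol (Treatment sessions, 1. Physical exercise), in two ways.

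- First statement: half of all the groups, called the FP-group, "will be randomly allocated sound and vibration feedback to help them to stay in a predetermined training zone".
- The remainder form the MP-group: "The other groups will not receive feedback but heart rate will still be measured".
- Second statement: "Assignment to FP-group and MP-group will alternate so equal numbers are obtained for statistical comparison".

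The wording makes whole groups the unit, although the labels expand to feedback participants and monitoring participants. Group size is given only under Socialising: "Socialising will take place in groups of 8 for the centre based participants". No size is given for online participants.

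The same Physical exercise section adds: "Heart rate monitors will be programmed by the research team". The Sample Size section powers two other things, the within-person change and a delivery-mode comparison ("The planned comparison between the community based /centre based groups (n=64"). It does not mention FP v MP. The Analysis section makes estimation of mean change with its confidence interval the principal analysis.

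**The concern.** A team following the first statement would draw a random sequence. A team following the second would give each group the opposite condition to the one before. These are different designs, and nothing elsewhere in the protocol says which applies.

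The difference matters because alternation removes concealment. The feedback is audible and felt, and the research team sets up the monitors, so the condition of the last group is no secret and the next follows from it. Groups appear to start one after another, since the Motivating adherence section speaks of each new group receiving an introductory talk. Entry dates have some play: people with modifiable exclusions are reconsidered later, and some are referred for medical review before they exercise. A participant thought keener or fitter could therefore be placed, even without intent, in a group whose condition is already known.

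At stake is what can be said about feedback. Compliance is one of the measures of success on the main outcome and cardiovascular fitness is a secondary outcome; feedback could plausibly affect either. The study also aims to establish treatment protocols and to size a later randomised trial. A report could call FP v MP randomised on the strength of the first statement when the groups had in fact been alternated. Analysis cannot reliably correct for selection on unmeasured traits such as motivation.

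**Working it through.** **1. The plan's own figures.** These reproduce (two-sided 5% assumed, as sidedness is not stated), and the point does not depend on them.
- Within-person change of 0.25 SD, 80% power: n = ((1.960 + 0.842)/0.25)² = 125.6, so 126; the plan has 128. Noncentral-t power at 128 is 80.2%.
- Two groups, 0.5 SD: n = 2 × ((1.960 + 0.842)/0.5)² = 62.8, so 63 per group; the plan has 64. Noncentral-t power at 64 per group is 80.1%.
- Precision: 1.979/√128 = 0.175 SD, as stated.

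Neither power statement concerns FP v MP, and the choice of allocation method changes none of these numbers.

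**2. Can the two statements be reconciled?**
- Random start, then alternation: only the first assignment would be random, and the protocol does not mention a random start.
- *Alternate* used loosely for *balanced*: this would fit the stated purpose, "so equal numbers are obtained for statistical comparison", but it is not what the sentence instructs.
- Random for one set of groups and alternating for another: both statements concern assignment to the same two conditions.

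None of these readings is supported by the text.

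**3. How predictable is each scheme?** The number of groups is not stated. Two illustrative values:
- 16 groups, if all 128 participants were in groups of 8 (128/8 = 16).
- 8 groups, if only the centre-based half is counted and 64 is read as the number per delivery mode (64/8 = 8).

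Possible sequences with equal numbers:
- 16 groups: C(16,8) = 12,870 under balanced random allocation; 2 under alternation.
- 8 groups: C(8,4) = 70; 2 under alternation.

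Expected share of assignments guessed correctly by someone who knows the past ones:
- Alternation, first assignment unknown: (0.5 + 15)/16 = 97% with 16 groups; (0.5 + 7)/8 = 94% with 8. After the first, it is 100%.
- One random block of 2m, guessing the condition with more places left: [m + 2^(2m−1)/C(2m,m) − 0.5]/2m. With m = 8: (8 + 32,768/12,870 − 0.5)/16 = 10.05/16 = 63%.
- Random blocks of 4 (m = 2): (2 + 8/6 − 0.5)/4 = 2.83/4 = 71%.

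A simulation of the two blocked schemes gave the same 63% and 71%. Blocking keeps the numbers equal and is still much less predictable than alternation. Revealing the condition only after membership is fixed deals with most of what remains, because the actual draw is then unknown while the group is being filled.

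**The case against.** The strongest reply is that little rests on FP v MP. Participants serve as their own controls, the main outcome is development and implementation of the programme, and the principal analysis is within-person change. The feedback comparison appears only in the one clause about statistical comparison. This stands, and it limits the severity.

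Second, the protocol does not say who forms the groups, whether they have any discretion, or when a group's condition is fixed relative to enrolment. If groups fill strictly in order of recruitment, steering would mean moving a person between neighbouring groups, which is a narrower route than alternation of individuals. This stands too: the comparison is open to selection bias, but neither its occurrence nor its size can be shown from the document.

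Third, a reader might infer that feedback is confounded with delivery mode, so that neither effect can be separated. The protocol gives no rule for assigning centre or online delivery, but nothing says that places are filled in turn or in step with the feedback sequence. Full confounding would be one supposed worst case and is not part of this point. Nor should the sample size for the delivery-mode comparison be read as applying to FP v MP.

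None of this reconciles the two sentences.

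**Conclusion.** The contradiction is real and lies within one paragraph. If the alternation sentence is followed, every assignment after the first is known in advance, whatever the number of groups, and FP v MP is not a randomised comparison. It is then open to selection bias of unknown size.

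Severity is moderate. Predictable allocation between FP and MP does not bias the overall within-person change, and the stated sample sizes are unaffected. The conclusion assumes only that the sequence and past assignments can be known to those placing participants, which the visible nature of the feedback makes likely. The counts of 16 and 8 groups are illustrative, because groups of 8 are stated only for centre-based participants.

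**What to change.** - Delete the alternation sentence.
- State that the unit of allocation is the group, and say what a group is for online participants.
- Allocate groups to FP or MP from a permuted-block random list, generated beforehand and kept from those who recruit or form groups. Reveal a group's condition only once its membership is fixed. Blocking gives the equal numbers that alternation was meant to secure.
- Where delivery mode is known beforehand, the list can be stratified by it. This is optional.

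If alternation is kept for practical reasons, remove the word *randomly* and report FP v MP as a non-randomised comparison.

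The cost is one rewritten paragraph and a list prepared in advance. No participants are added, and the sample size and the intervention do not change. The choice has to be made before the first group is assigned, since it cannot be repaired afterwards.

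### The effort-based training rate is written for beta-blocker users only, so an FP-group participant on another drug that lowers exercise heart rate would be given a zone demanding more effort than intended

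*Protocol*

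**What the plan says.** Three parts of the Protocol bear on this.

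- **Default zone** (Treatment sessions, 1. Physical exercise). The moderate zone is 65-77% of maximum heart rate, worked out for every participant from 220 minus age. In the FP-group the monitor "alerts the patient when heart rate is outside the preset parameters". The MP-group has heart rate recorded, receives no alerts and is taught to pace by perceived effort.
- **Exception** (same section). "Patients taking beta blocker medication will exercise at a heart rate equivalent to a specific effort", namely 14 on the Borg scale, "as these medications lower heart rate and result in sub optimum training when training zones are calculated as described above". The rate is individual: "The relevant rate will be determined during the initial supervised walking sessions".
- **Admission** (Methods, paragraph closing the exclusion criteria). People on drugs that affect heart rate may enter after three months of stable dosing. The wording is not limited to beta blockers. The stated purpose is to keep the fitness measurements free of drug artefact; it does not concern the training zone.

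The exercise section also describes contact and monitoring: "They will receive home visits and supervision at sessions 1, 3, 8, 14 and 20"; "They will also receive regular weekly telephone contact to provide support and monitor progress"; "Heart rate monitors will be programmed by the research team".

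**The concern.** The exception is narrower than its own reason. The Protocol accepts that an age-predicted zone does not suit someone whose heart rate is lowered by a drug, yet corrects it for one drug class. At entry it recognises a wider class. A participant on some other drug that lowers exercise heart rate is admissible and, as the text stands, falls under the default zone.

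This matters in the FP-group because the alerts act on heart rate. If the drug holds heart rate down, the lower alert prompts more effort than planned, and the upper alert sounds only after the intended 77% level of effort has been passed. The Protocol gives that ceiling some weight. The introduction links work at 70-85% of maximum to injury and drop-out. The step height in the fitness test was reduced because the original height pushed heart rate above 77%.

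At stake are treatment fidelity and comfort, and possibly safety, for a few participants. MP-group participants pace by effort and are not driven by the zone.

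**Working it through.** **No plan figure to reproduce.** The Protocol gives no number for a drug effect or for how many participants take such drugs. The text was compared first; the arithmetic then illustrates the size.

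**Who falls under which rule (FP-group)**

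| Participant | Admissible? | Zone as written |
|---|---|---|
| No heart-rate drug | Yes | 65-77% of 220 - age |
| Beta blocker, stable 3 months | Yes | Rate at Borg 14 |
| Other drug lowering exercise heart rate, stable 3 months | Yes | 65-77% of 220 - age |

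The third row is the gap.

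**Inputs.** From the Protocol: limits of 65% and 77%, and maximum = 220 - age. Assumed: age 75 (65 and 85 as a check) and a drug reduction d of 5, 10 or 20 bpm.

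**Zone at age 75.** Maximum = 220 - 75 = 145 bpm. Lower limit = 0.65 × 145 = 94.25. Upper limit = 0.77 × 145 = 111.65. Width = 17.4 bpm.

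**What those limits stand for on the drug.** Two simple models were used:

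- Fixed shift: heart rate at a given effort is d lower, so effort = (limit + d) / 145.
- Lowered maximum: the maximum falls to 145 - d, so effort = limit / (145 - d).

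| d (bpm) | Fixed shift, bottom to top | Lowered maximum, bottom to top |
|---|---|---|
| 0 | 65.0-77.0% | 65.0-77.0% |
| 5 | 68.4-80.4% | 67.3-79.8% |
| 10 | 71.9-83.9% | 69.8-82.7% |
| 20 | 78.8-90.8% | 75.4-89.3% |

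Example for d = 20: (111.65 + 20) / 145 = 90.8%, and 111.65 / 125 = 89.3%.

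**Share of the zone above the intended ceiling.** Fixed shift, d / 17.4: 29%, 57% and 100% (capped). Lowered maximum, 0.77d / 17.4: 22%, 44% and 89%. So at 5-10 bpm part of the zone still lies at the intended effort; at 20 bpm little or none does.

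**Sensitivity to age (top of zone, d = 5, 10, 20).** Age 65: 80.2, 83.5, 89.9% (shift) or 79.6, 82.3, 88.4% (lowered maximum). Age 85: 80.7, 84.4, 91.8% or 80.0, 83.2, 90.4%. Age makes little difference; the assumed d drives the result. Under both models any d above zero puts the top above 77%.

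**The case against.** The case for leaving the text alone has substance.

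- **No other drug is named.** The entry rule speaks of effects on heart rate in either direction, and a drug that does not lower heart rate during exercise would not matter. This stands: the point is conditional.
- **The two rules have different aims.** The stable-dosing rule protects fitness measurements, and the Borg rule rests on a source that the Protocol applies to beta blockers. Different scopes need not contradict each other. This stands against calling it a contradiction. The reason given for the exception is nevertheless lowered heart rate, and that is not special to one class.
- **Safeguards exist.** Exclusion criterion 4 removes people whose medical problems prevent safe exercise at 65-77% of predicted maximum, the same age-based scale. The PAR-Q screens for low risk and can lead to medical review and PARmed-X guidance. The team programs the monitors, sessions 1 and 3 are supervised, and there are weekly calls. These reduce the risk. But criterion 4 is framed by medical problem, not by drug; PARmed-X follows where the PAR-Q indicates it; visits cover 5 of 36 sessions; and the logger works so that "heart rate data during physical activity is captured for later analysis", which does not reset a zone during a session. None tells the team to program a different zone.
- **The sizes are assumed.** Correct; they are illustrations.

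A reader might infer that admitted participants will in fact be over-exerted. The documents do not support that: they do not show that such users will enrol, and the Protocol itself speaks only of sub-optimal training. Over-exertion is an inference from how the alerts work. Nor can a reader conclude that the trial's results are undermined: no sample-size figure or main analysis depends on this rule.

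**Conclusion.** The point holds in conditional form. If an FP-group participant takes a drug other than a beta blocker that lowers exercise heart rate, the rule as written gives a zone that demands more effort than the intended 65-77%. Under an assumed reduction of 5-20 bpm at age 75, the top of that zone corresponds to about 80-91% of maximum. The size depends on that assumption and on the two simple models used; the direction depends only on the drug lowering heart rate during exercise. The number of participants concerned cannot be derived from the Protocol. This is an optional, inexpensive improvement to treatment fidelity and safety.

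**What to change.** In Treatment sessions, 1. Physical exercise, widen the exception to read *beta blocker or other medication that lowers exercise heart rate*. Identify these participants when medication is checked for the three-month stable-dosing rule, and set their rate at Borg 14 in the initial supervised walking sessions, as already planned for beta-blocker users.

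The cost is one phrase. It needs no extra patients, visits or forms, because the sessions are already planned and the stable-dosing rule already requires knowing who takes such drugs. The downside is small but real: a few more participants would have an effort-based zone, the Protocol does not show that Borg 14 equals 65-77% of maximum, and it applies its cited source to beta blockers only. The change therefore brings these participants under the existing rule without guaranteeing the target intensity. It does not address drugs that raise heart rate.
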